8.5.5 Study Drug Administration

SOL-116 will be administered as abdominal SC injection(s). The injection volume will be no more than 2.0 mL per injection. The number of SC injections given to administer the single dose in Cohort 2 to Cohort 7 may be increased to up to 4 injections.

Subjects/patients will not be allowed to eat or drink (except water) from 10 hours prior to the administration of study drug or placebo.

All study drugs will be dispensed by the Investigator or a person supervised by the Investigator. The time of administration of SOL-116 or placebo will be recorded in the eCRF.

In Part 3, the same applies but 4 dose administrations (with maximum 4 injections per occasion) will be administered with 28 days' interval (in MD1).

In Part 2, there should be at least 24 hours between administration of SOL-116 and the preceding MTX dose and at least 24 hours between administration of SOL-116 and the subsequent MTX dose.

8.5.6 Storage and Return of Study Drug

Upon receipt of the study drugs, the responsible pharmacist or her designee will inspect all study drugs for completeness. Subsequently, he/she must immediately return the enclosed acknowledgement of receipt form; duly completed and signed (the date of receipt must be noted).

The pharmacist is responsible for storage of the study drug at the study site in an appropriate lockable room at 2–8 °C. The drug will be stored according to the instructions provided by the Sponsor. Only the pharmacist or his/her designee, who are otherwise not involved in the study, will handle the study drug.

A Drug Preparation Protocol as well as a Drug Accountability Record must be kept current and should at least contain the following information:

- Subject/patient number for whom the drug was prepared
- Initials and date of the person who prepared the study drug
- Date(s) on which drug was prepared and quantity of the drug prepared

The inventory must be available for verification by the clinical research associate (CRA)/monitor.

After Sponsor confirmation, all unused investigational material (drugs and packaging) must be returned to the Sponsor or destroyed by the site on termination of the study and after a drug accountability check by the CRA/monitor, listing the following:

- All SOL-116 administered
- All unused SOL-116
- All SOL-116 returned at the end of the study, and the date of return/destroyed by the site

The pharmacist will be responsible for the inventory and accountability of all Clinical Trial Material, exercising accepted pharmaceutical practices. An accurate, timely record of the Clinical Trial Material will be maintained. Only after completion of the study (to avoid breaking the blind), the Clinical Trial Material and the inventory will be available for inspection by the designated representatives of Lipum AB upon request. The original Drug Preparation Protocol and Drug Accountability Record are considered as source data and will be archived at the site.

8.6 Safety Review Committee

The study will be monitored by an SRC. The SRC is intended to ensure that the study drug does not pose undue risk to subjects/patients. Safety, tolerability and available PK data up to 14 days post-dose of at least 6 evaluable subjects (subject assessed as pharmacokinetically evaluable at Day 14) will be assessed by the SRC prior to ascending from one dose-level cohort to the next-higher dose-level cohort. For Cohort 2 onwards, cumulative PK data will also be considered. Key PK parameters for dose escalation are C_{max} ($\mu\text{g}/\text{mL}$) and AUC ($\mu\text{g}/\text{mL}^*\text{h}$). A

dose increment of 3 will never be exceeded in selecting the next dose level. Prior to Cohort 3 and thereafter, the SRC will also consider dose linearity.

For Part 3, the same applies but data up to 28 days post last dose will be collected and assessed at the SRC.

The SRC will be composed of the following core individuals:

- Principal Investigator(s) or delegate(s) (delegation only when a Principal Investigator is not available);
- Lipum AB chief medical officer or delegate (must be a physician);
- QPS pharmacokineticist;
- Other internal or external experts may be invited to participate in the review or may be consulted.

8.7 Dose Escalation Strategy

8.7.1 Determination of Dose Escalation/Subsequent Dosing

For Part 1: The decision to escalate to the next dose level will not take place until the SRC has reviewed the blinded safety and tolerability data, including but not limited to vital signs, ECG results, clinical laboratory tests, and AEs, up to and including 14 days post-dose of at least 6 evaluable subjects (subject assessed as pharmacokinetically evaluable at Day 14). For Part 2: The same applies as for Part 1 but will include 21 days data for safety/PK review.

For Part 3: The decision to escalate to the next dose level will not take place until the SRC has reviewed the blinded safety and tolerability data, including but not limited to vital signs, ECG results, clinical laboratory tests, and AEs, up to and including 28 days (i.e., T_{max} plus one half-life) post last dose of at least 6 evaluable subjects (subject assessed as pharmacokinetically evaluable at Day 28 post last dose).

Additionally, for all parts, an interim PK analysis of available serum SOL-116 concentration data will be reviewed as part of the dose escalation assessment. Any available blood PK data will be reviewed as part of the dose escalation assessment.

After the review of each dose level, the SRC will make one of the following determinations:

- To continue with the study as planned. The SRC agrees that adequate safety and tolerability have been demonstrated in accordance with the dose-escalation and stopping criteria).
- To continue with the study as planned and evaluate additional or alternate time points for safety evaluations. Additional time points for existing safety procedures requiring blood collection may be added, provided that the additional time points do not result in the additional collection of more than 15 mL of blood. For the addition of safety procedures that would require blood collection more than 15 mL, an EC-approved protocol amendment and Informed Consent Form is required.
- To continue with the study by:
 - o Repeating a dose level.
 - o Selecting an alternative dose level between the current dose level and the next planned dose level.
 - o Selecting an alternative dose level between the current dose level and any previous lower dose level.

The SRC, Principal Investigator(s) or Lipum AB may terminate dose escalation at any time if continuing to a higher dose level would jeopardize the safety of the subjects/patients. SRC

reports will be submitted to the Independent Ethics Committee (IEC) for approval of the planned dose escalation and for approval to proceed to the next cohort. After completion of all healthy subject cohorts, the report to the IEC on proceeding to the patient cohort will also include a cumulative interim report and a revised structured risk analysis, as applicable.

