3. If the clinic visit is extended up to and including Day 6, Visit 4 will not take place. In that case, all assessments including blood sampling scheduled for Visit 4 will be performed on Day 6, at the discretion of the Investigator.
4. Study site should make a **phone follow-up with subject approximately 3 to 7 days after dose** to follow up adverse events and/or medication.
5. Not to be performed when this assessment was done within 3 weeks prior to dosing and result is available.
6. The PI must review Day -1 safety lab results prior to dosing.
7. Triplicate at Screening and on Day -1. On Day 1: 1 and 4 hours post-dose.
8. From 1 hour pre-dose until 6 hours post-dose.
9. Serum at Screening, urine at all other timepoints.
10. Only collected and analysed when the subject has given consent for the collection and future analysis of this sample in the informed consent form. Pre-dose on Day 1 and Days 85, 92 and 169.
11. Fasting glucose determined at Screening only. Lipid status determined only at Screening and Day 169 only (10 hours' fasting at both occasions). No pancreatic lipase on Day 92.

12. If medically indicated and/or based on emerging data, the clinic stay may be extended up to Day 7.
13. Starting from first study drug administration.
14. On Day 1: Prior to dosing and 1 and 4 hours post-dose. After the other doses: Prior to dosing and 4 hours post-dose.
15. Day 92 only
16. Assessed for four (4) hours after each injection and thereafter as needed.
17. Prior to dosing and 4 hours post-dose.
18. Pre-dose, 4 and 24 hours post-dose
19. Pre-dose only.
20. Pre-dose and 4 hours post dose.
21. Day 113 only.
22. Day 88 only
23. Days 92 and 113 only.
24. Up until first study drug administration.

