6.1.3 Clinical Experience with SOL-116 (current study)

To date, Part 1 has been concluded. Five cohorts with 8 healthy subjects (male and female) per cohort have been administered SOL-116 or placebo (6 active and 2 placebo), up to 6.075 mg/kg single dose. There were 25 males and 15 females enrolled, age range 22 to 64 years. No subjects dropped out, few adverse events and no serious adverse event (SAE) were reported. There were no clinically relevant changes from baseline reported on the following: vital signs, ECG parameters, telemetry, clinical laboratory, physical examination. The serum SOL-116 exposure (AUC, C_{max}) increased in an approximately dose-proportional manner.

In Part 2, the enrolment of rheumatoid arthritis (RA)-patients is currently ongoing. Part 3, with multiple dosing is ongoing.

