8.2 Overall Study Design

This is a randomized, double-blind, placebo-controlled phase I, first-in-human (FIH) study designed to evaluate the safety, tolerability and PK of single SC ascending doses of SOL-116 in healthy subjects and adult RA patients (Parts 1 and 2) and multiple SC doses in healthy subjects (Part 3).

The study will be monitored by a Safety Review Committee (SRC). The intent of the SRC is to ensure that treatment does not pose undue risk to subjects/patients. Safety, tolerability and

available PK data will be assessed by the SRC after each cohort before ascending to the next dose level. Based on SRC recommendation, the visit schedule may be adjusted.

Part 1

Eligibility will be assessed during a screening period of up to 28 days. For the treatment period, subjects will check into the clinic one day prior to dosing (Day -1). On Day 1, all subjects will receive SOL-116 in a fasted state (after an overnight fast of at least 10 hours). Subjects will be released from the clinic on Day 4, after all required study procedures are completed and if medically justified. If medically indicated and/or based on emerging data, the clinic stay may be extended up to Day 7. Subjects will return to the clinic for 6 ambulant visits up to Day 63. Subjects will return to the clinic on Day 90 for an EOS/follow-up visit.

Up to 5 single doses are planned to be tested in 5 cohorts of 8 healthy subjects (6 active, 2 placebo) (Cohort 1 to Cohort 5). One additional¹ cohort (Cohort 6) of 8 healthy subjects (6 active, 2 placebo) may be added based on emerging data, i.e. in total 40 or 48 subjects will be randomized and dosed.

The starting dose in Cohort 1 will be 0.075 mg/kg SOL-116 given as a single SC injection. The actual dose for Cohort 2 to Cohort 5 and the dose regimen for the optional additional cohort of healthy subjects (Cohort 6) will be based on the safety and PK results of all preceding cohorts. Furthermore, based on the safety and PK results of all preceding cohorts the number of SC injections given to administer the single dose in Cohort 2 to Cohort 6 may be increased to up to 4 injections. The maximum dose increment will be 3. The highest dose to be tested in man will not exceed a dose predicted to generate exposures above those at NOAEL in the monkey (plasma concentrations of 1240 µg/mL (C_{max}) or an AUC_{0-168h} of 164000 µg/mL*h).

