8.7.2 Dose Escalation Stopping Criteria

- One (1) or more subjects who receive SOL-116 experience a SAE which is considered to be related to the study medication.
- Two (2) or more subjects who receive SOL-116 have QTc prolongation, defined as an average absolute (regardless of baseline value) QTcF >500 msec or an increase of QTcF >60 msec above baseline, confirmed by repeated ECG after at least 5 minutes, and determined post-dose.
- Two (2) or more subjects who receive SOL-116 exhibit hypotension, defined as resting supine diastolic blood pressure <40 mmHg, an asymptomatic or symptomatic fall in systolic blood pressure to below 80 mmHg, persisting for at least 10 minutes on repeated assessment.
- Two (2) or more subjects who receive SOL-116 exhibit hypertension, defined as an increase in resting systolic blood pressure to above 180 mmHg, persisting for at least 10 minutes, or an increase in resting diastolic blood pressure to above 105 mmHg, persisting for at least 10 minutes.
- Two (2) or more subjects who receive SOL-116 exhibit tachycardia, defined as resting supine heart rate >130 beats per minute, persisting for at least 10 minutes.
- Two (2) or more subjects who receive SOL-116 exhibit symptomatic bradycardia, defined as heart rate <40 beats per minute, or asymptomatic bradycardia, defined as resting supine heart rate <30 beats per minute while awake, persisting for at least 10 minutes.
- One (1) or more subjects who receive SOL-116 fulfills Hy's law, defined as aspartate aminotransferase (AST) or alanine aminotransferase (ALT) $\geq 3 \times$ upper limit of normal (ULN) and total bilirubin $\geq 2 \times$ ULN, in the absence of a significant increase in alkaline phosphatase (ALP) and in the absence of an alternative diagnosis that explains the increase in total bilirubin (confirmed by repeating within 24 hours).
- Two (2) or more subjects who receive SOL-116 exhibit ALT, total bilirubin, or ALP $>3 \times$ ULN accompanied by significant increase in other liver function test (confirmed by repeating within 24 hours).
- Two (2) or more subjects who receive SOL-116 exhibit renal toxicity, defined as serum creatinine $\geq 1.5 \times$ ULN (confirmed by repeating within 24 hours).
- Two (2) or more subjects who receive SOL-116 exhibit hematologic toxicity, defined as one or more of the following (confirmed by repeating within 24 hours):
 - Leukocyte count $<2.5 \times 10^9/L$
 - Neutrophil count $<1.0 \times 10^9/L$

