10.9 Interim Safety Report

For Parts 1 and 2, the interim safety analysis will be conducted by the SRC on safety/tolerability and available PK data up to and including 14 days post-dose after completion of at least 6 evaluable subjects per treatment group (subject assessed as pharmacokinetically evaluable at Day 14). For Part 3, the interim safety analysis will be conducted by the SRC on safety/tolerability and available PK data up to and including 28 days post last dose after completion of at least 6 evaluable subjects per treatment group (subject assessed as pharmacokinetically evaluable at Day 28 post last dose).

Based on the results of the interim analysis (including but not limited to AEs, vital signs, ECGs, and clinical laboratory tests), a decision will be taken by the Principal Investigator(s) and Lipum AB whether the next cohort can start with the planned dose. This decision will only be made after discussion between the Principal Investigator(s) and the Sponsor and after mutual agreement and must be submitted to the IEC/IRB for approval before dosing can proceed.

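### Part 3 escalation rests on vital signs and laboratory tests to 28 days after the last dose (Day 113), but the schedule has neither between Day 92 and Day 169

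*Protocol*

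**What the plan says.** Three Protocol sections set the Part 3 gate.

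- Section 8.7.1 requires SRC review of "vital signs, ECG results, clinical laboratory tests, and AEs, up to and including 28 days" after the last dose, in at least 6 evaluable subjects.
- Section 8.6: "For Part 3, the same applies but data up to 28 days post last dose will be collected and assessed at the SRC".
- Section 10.9 has the SRC assess "safety/tolerability and available PK data up to and including 28 days post last dose after completion" of at least 6 evaluable subjects, and names the inputs to the decision: "Based on the results of the interim analysis (including but not limited to AEs, vital signs, ECGs, and clinical laboratory tests").

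Section 8.2 puts the MD1 doses on Days 1, 29, 57 and 85. In Table 5-3, Visits 12-17 (Days 92, 95, 99, 113, 140 and 154) share one column. The entries in that column for vital signs and for the safety laboratory row carry footnote 15, which confines them to Day 92. The cytokine entry in the same column carries a different footnote: "23. Days 92 and 113 only". The next entry for both safety rows is Day 169. The 12-lead ECG row has no entry between Day 85 (4 hours post-dose) and Day 169.

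**The concern.** The text promises the SRC data that the schedule does not generate. The criteria in 8.7.2 for liver, kidney, blood counts, blood pressure and heart rate are defined on measured values; for example, "Two (2) or more subjects who receive SOL-116 exhibit hematologic toxicity, defined as one or more of the following" is followed by leukocyte, neutrophil and platelet thresholds. Adverse-event questioning on Day 113 will not detect an asymptomatic fall in neutrophils or a rise in ALT. If such a change arose after Day 92, the SRC would not see it at the escalation decision, and the next scheduled sample would be on Day 169.

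The gap falls after the dose to which the gate is tied. Doses 1, 2 and 3 each have laboratory tests and vital signs 28 days later, because the next pre-dose set supplies them. Dose 4 does not. The ethics committee approves escalation on the SRC's report, under text that describes wider coverage than the plan provides.

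**Working it through.** **Is the table read correctly?** Table 8-5 gives an independent check. Part 3 laboratory days read from Table 5-3 are Screening, -1, 4, 8, 29, 57, 85, 88, 92 and 169, which is 10. Table 8-5 budgets hematology at 3.0 mL x 10 and coagulation at 2.7 mL x 10. The same reading gives 6 antibody samples (Days 1, 29, 57, 85, 113, 169), 10 cytokine samples and 20 PK samples, all matching Table 8-5, and the table's lines sum to its stated 312.5 mL. Chemistry is listed at 11, one more than hematology. The same excess of one appears in Tables 8-3 and 8-4 (12 against 11), so it does not point to a Day 113 safety set.

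**Day arithmetic (MD1).**
- Review cut-off: 85 + 28 = Day 113.
- Last scheduled laboratory tests and vital signs before it: 92 - 85 = 7 days after dose 4.
- Part of the window with neither: 113 - 92 = 21 of 28 days.
- Gap to the next set: 169 - 92 = 77 days; that set is 169 - 85 = 84 days after dose 4.

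**Scheduled assessments by dose (days after that dose, before the next dose is given):**

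| Dose (day) | Laboratory tests | Vital signs (beyond dosing day) |
|---|---|---|
| 1 (Day 1) | 3, 7, 28 | 1, 3, 7, 28 |
| 2 (Day 29) | 28 | 28 |
| 3 (Day 57) | 28 | 28 |
| 4 (Day 85) | 3, 7, then 84 | 1, 3, 7, then 84 |

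**Position relative to the peak.** Section 8.7.1 explains 28 days as Tmax plus one half-life. With the half-life of about 19 days in section 6.3.4, the implied Tmax is 28 - 19 = about 9 days. The Day 92 set, at 7 days, therefore falls around or before the dose-4 peak.

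**How far does Day 85 stand in?** Assume linear one-compartment kinetics, with r = 2^(-28/half-life) and fraction of steady state after n doses = 1 - r^n. For a half-life of 19 days, r = 2^(-28/19) = 0.360. The fractions for n = 1 to 4 are 0.640, 0.870, 0.953 and 0.983. Dose 3 relative to dose 4 is 0.953/0.983 = 0.970. For assumed half-lives of 15 and 25 days the ratio is 0.985 and 0.945.

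**Comparison with Parts 1 and 2.** Their cut-off visits (Day 14 in Table 5-1, Day 21 in Table 5-2) schedule both vital signs and laboratory tests. They share the ECG gap: neither has a 12-lead ECG between Day 4 and Day 90.

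**The case against.** The strongest reply is that little is lost. The Day 85 pre-dose set is a 28-day check at about 97% of dose-4 exposure. With Days 29 and 57 the SRC has three such sets per subject, plus adverse events and PK to Day 113. What goes unseen is an asymptomatic change that first appears 8 to 28 days after dose 4, having been absent at 28 days after each earlier dose. This stands, and it limits the seriousness of the point. It does not supply data from after dose 4.

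The 21-day figure also needs care. Doses 2 and 3 have only their 28-day set, so dose 4 has more post-dose time points than either. The Day 92 visit has a window of 3 days either way, so the last set could fall 10 days after a Day 85 dose. What distinguishes dose 4 is the missing assessment at the cut-off, not sparse sampling in between.

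The review period could be read as a data cut-off, meaning whatever was scheduled by then. The ECG wording for Part 1 lends this some support. Against it, 8.6 says the data will be collected, 10.9 attaches availability to PK rather than to safety, and Parts 1 and 2 schedule both assessments at their cut-offs.

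Finally, the plan is flexible. Section 8.2 lets the SRC move the review time point on PK grounds, and "Based on SRC recommendation, the visit schedule may be adjusted". Unscheduled tests are also possible. These are options, and none puts the assessments on the schedule.

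**Conclusion.** The concern holds. As written, the Part 3 gate requires vital signs and laboratory tests to Day 113, while the schedule ends them at Day 92 and resumes on Day 169. That leaves 21 of 28 days after dose 4 with neither, including the cut-off visit itself. No reason is given, and subjects are already at the clinic for venepuncture on that day.

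It should be corrected, but it does not leave the SRC without safety information: the Day 85 set is a close surrogate and adverse-event follow-up is continuous. The figure of about 97% depends on assumed linear one-compartment kinetics (94.5% to 98.5% for half-lives of 25 to 15 days). The exact days apply to MD1; MD2 may use another interval. The documents say "Part 3, with multiple dosing is ongoing", but not whether any MD1 subject is still before Day 113.

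**What to change.** **Preferred.** On the vital-signs and safety-laboratory rows of Table 5-3, Visits 12-17, replace footnote 15 with the existing footnote 23. Apply it to MD1 subjects who have not passed Day 113, and to the equivalent 28-day visit in MD2. No escalation is planned after MD2, so there it would serve the SRC meeting that follows every cohort.

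**If the schedule is kept, or MD1 has passed Day 113.** Reword 8.6, 8.7.1 and 10.9, and state in the SRC report to the ethics committee, that after the last dose laboratory tests and vital signs extend to 7 days and 12-lead ECG to 4 hours. Because the ECG gap is common to all parts, handle it in the wording or add an optional ECG at the cut-off visit.

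**Cost.** One laboratory set is 4.5 + 3.0 + 2.7 = 10.2 mL, taking the Part 3 total from 312.5 to 322.7 mL (10.2/312.5 = 3.3%), plus one set of vital signs at an existing visit. Section 12.1.1.2 treats changes to study assessments as substantial, needing ethics committee and authority approval. Section 8.7.1 does let the SRC, after reviewing a dose level, add time points for existing safety procedures up to 15 mL, and requires an amendment only above that. The 10.2 mL fits, but because that power follows a review it may not reach MD1 before its own gate, so an amendment is the secure route there. The wording option needs no sampling but still needs a text amendment.

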8.7.2 Dose Escalation Stopping Criteria

- One (1) or more subjects who receive SOL-116 experience a SAE which is considered to be related to the study medication.
- Two (2) or more subjects who receive SOL-116 have QTc prolongation, defined as an average absolute (regardless of baseline value) QTcF >500 msec or an increase of QTcF >60 msec above baseline, confirmed by repeated ECG after at least 5 minutes, and determined post-dose.
- Two (2) or more subjects who receive SOL-116 exhibit hypotension, defined as resting supine diastolic blood pressure <40 mmHg, an asymptomatic or symptomatic fall in systolic blood pressure to below 80 mmHg, persisting for at least 10 minutes on repeated assessment.
- Two (2) or more subjects who receive SOL-116 exhibit hypertension, defined as an increase in resting systolic blood pressure to above 180 mmHg, persisting for at least 10 minutes, or an increase in resting diastolic blood pressure to above 105 mmHg, persisting for at least 10 minutes.
- Two (2) or more subjects who receive SOL-116 exhibit tachycardia, defined as resting supine heart rate >130 beats per minute, persisting for at least 10 minutes.
- Two (2) or more subjects who receive SOL-116 exhibit symptomatic bradycardia, defined as heart rate <40 beats per minute, or asymptomatic bradycardia, defined as resting supine heart rate <30 beats per minute while awake, persisting for at least 10 minutes.
- One (1) or more subjects who receive SOL-116 fulfills Hy's law, defined as aspartate aminotransferase (AST) or alanine aminotransferase (ALT) $\geq 3 \times$ upper limit of normal (ULN) and total bilirubin $\geq 2 \times$ ULN, in the absence of a significant increase in alkaline phosphatase (ALP) and in the absence of an alternative diagnosis that explains the increase in total bilirubin (confirmed by repeating within 24 hours).
- Two (2) or more subjects who receive SOL-116 exhibit ALT, total bilirubin, or ALP $>3 \times$ ULN accompanied by significant increase in other liver function test (confirmed by repeating within 24 hours).
- Two (2) or more subjects who receive SOL-116 exhibit renal toxicity, defined as serum creatinine $\geq 1.5 \times$ ULN (confirmed by repeating within 24 hours).
- Two (2) or more subjects who receive SOL-116 exhibit hematologic toxicity, defined as one or more of the following (confirmed by repeating within 24 hours):
 - Leukocyte count $<2.5 \times 10^9/L$
 - Neutrophil count $<1.0 \times 10^9/L$
 - Platelet count $<75 \times 10^9/L$

In addition, the SRC may stop dose escalation at any time if the SRC determines that dose escalation would pose undue risk to subjects. If dose escalation is not stopped, the SRC may recommend ascending to the planned next-higher dose level cohort, ascending to a dose level

lower than the planned next-higher dose level cohort, or a repeat dosing at the current dose level.

The safety and available PK data will be reviewed by the SRC. For the PK results, this will be done in a blinded manner (e.g., without subject identifiers or using reblinded subject numbers), but if the SRC considers it necessary due to a safety concern, individual subject data or an entire cohort's data may be unblinded to the SRC to enable decision-making. Before any such unblinding, the reason for unblinding will be documented.

SRC reports will be submitted to the IEC for approval of dose escalation.

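### A stopping criterion met during Part 2 or Part 3 ends dose escalation but does not, by rule, pause the remaining multiple doses or the undosed RA patients

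*Protocol*

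**What the plan says.** Protocol 8.7.2 sets ten criteria under a heading about stopping dose escalation. Two need a single subject: a Hy's-law result, and "One (1) or more subjects who receive SOL-116 experience a SAE which is considered to be related to the study medication". The other eight need two or more subjects on SOL-116. The section then adds "In addition, the SRC may stop dose escalation at any time if the SRC determines that dose escalation would pose undue risk to subjects". In 8.7.1 the SRC, a Principal Investigator or the sponsor "may terminate dose escalation at any time if continuing to a higher dose level would jeopardize the safety of the subjects/patients".

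Section 8.7.1 also states: "After the review of each dose level, the SRC will make one of the following determinations". Three follow: continue as planned, continue with added or alternative safety time points, or continue at a repeated or alternative dose level.

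On timing, 8.2 places the SRC meeting after a cohort completes dosing. Part 1 review uses 14 days of data from at least 6 evaluable subjects. For Part 2, 8.7.1 says "The same applies as for Part 1 but will include 21 days data for safety/PK review" (10.9 still gives 14 days). Section 8.6 adds: "For Part 3, the same applies but data up to 28 days post last dose will be collected and assessed at the SRC".

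Section 6.1.3 gives the state of the trial: "In Part 2, the enrolment of rheumatoid arthritis (RA)-patients is currently ongoing. Part 3, with multiple dosing is ongoing".

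**The concern.** The criteria suit Part 1, where each cohort received one dose and the next decision was whether to go higher. Parts 2 and 3 differ. Cohort 7 doses patients over time at one fixed level. MD1 gives each subject four injections over 12 weeks, and exposure builds up without any step that the protocol calls escalation. A rule that only prevents a higher dose has nothing to act on inside these cohorts.

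This is a first-in-human, first-in-class antibody with a half-life of about 19 days (6.3.4) and no antidote (13.1.10). A dose cannot be taken back, whereas a pause can be lifted. Part 1 gave single doses only, so it says nothing about repeated exposure. Part 3 drug is prepared at the contract research site and Part 2 drug at a hospital pharmacy (8.5.2), so a signal in one part needs a rule that reaches the other.

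**Working it through.** The plan states no operating characteristics for its stopping rules, so there is no figure to reproduce. The check is a reading of what each provision does, followed by counts.

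**Provisions that could stop dosing within a cohort**

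| Provision | Acts on | Tied to the 8.7.2 criteria? |
|---|---|---|
| 8.7.2 criteria and SRC stop | dose escalation | yes |
| 8.7.1 SRC, investigator or sponsor stop | dose escalation | no |
| 8.7.1 determinations | all three continue the study | no pause listed |
| 8.7.3 | allows reduced or repeat levels after escalation ends | yes |
| 8.2 sentinel check | the other 6 subjects, on the first 48 hours, by investigator judgement | no |
| 12.1.9 | the affected subject only, discretionary | no |
| 8.8.1, 12.1.10 | suspension or termination, discretionary | no |
| 12.1.1.3 | immediate safety change by an investigator, discretionary | no |
| 9.2.2.4 | 24-hour SAE reporting; passes on information | no |

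Only one of the sentinel pair is on SOL-116, so that pair cannot meet any of the eight two-subject criteria. In Part 3 the sentinel check is described for starting the other six subjects, not for doses 2 to 4.

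**Doses outstanding in MD1.** Doses fall on Days 1, 29, 57 and 85, with 6 active subjects (8.2). The SRC data cut is Day 85 + 28 = Day 113. If all six have had k doses, the active doses still due are 6 × (4 − k):

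- after dose 1: 18 (15 if the affected subject is discontinued)
- after dose 2: 12 (10)
- after dose 3: 6 (5)

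MD2's schedule is open, so its counts may differ.

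**Part 2.** After the sentinel pair (1 active, 1 placebo), 8 − 2 = 6 patients are undosed, 6 − 1 = 5 of them active. Scheduled review needs at least 6 evaluable patients with 21 (or 14) days of data, so at most 2 of 8 could then be undosed.

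**Exposure.** With instant absorption, r = 2^(−28/19) = 0.360. Exposure after dose 4 relative to dose 1 is (1 − r⁴)/(1 − r) = 1.536. Then 3.0 × 1.536 = 4.61 mg/kg-equivalent, and 4.61/6.075 = 76% of the highest single dose. Section 8.7.1 equates 28 days with Tmax plus one half-life, which implies Tmax of about 28 − 19 = 9 days. First-order absorption with that Tmax gives peak accumulation of about 1.65, and 3.0 × 1.65/6.075 is about 82%. Both figures assume dose proportionality. The total dose is 4 × 3.0 = 12 mg/kg, about twice 6.075.

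**Chance that a one-subject criterion is met among 6 active subjects,** 1 − (1 − p)⁶, at assumed rates p: 5.9% at 1%, 11.4% at 2%, 26.5% at 5%. Part 1 had no SAE in 5 × 6 = 30 active subjects, so the one-sided 95% upper limit is 1 − 0.05^(1/30) = 9.5%.

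**False pauses if all 8 subjects are counted blinded**

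- One-subject criterion, per cohort, 1 − (1 − p)⁸: 3.9% at 0.5%, 7.7% at 1%, 14.9% at 2%.
- Two-subject criterion at 2%: P(≥2 of 8) = 1.03%. Over two cohorts, 1 − (1 − 0.0103)² = 2.06%. Over eight independent criteria, 1 − (1 − 0.0206)⁸ = 15.3%.
- The same, pooled over 16 subjects: P(≥2 of 16) = 3.99%, and 1 − (1 − 0.0399)⁸ = 27.8%.

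**The case against.** The strongest reply is that the people who would act already can. The SRC's core members include the Principal Investigators and the sponsor's chief medical officer (8.6). The sponsor and investigators can suspend or terminate the study, and an investigator can make an immediate safety change. Related, unexpected SAEs are expedited to authorities, the ethics committee and investigators (9.2.2.4). Table 5-3 schedules vital signs, ECG and laboratory tests before doses 2 to 4. In Part 1, "No subjects dropped out, few adverse events and no serious adverse event (SAE) were reported". On this view a competent team would stop dosing without being told to.

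Much of that stands, and it rules out several stronger readings.

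- A reader might infer that dosing could not be stopped. It could, by discretion.
- A reader might infer that the SRC can act only on escalation. It may also adjust visits, add safety time points, repeat or lower a dose level, and unblind. None of these is a stated power to pause dosing within a cohort.
- A reader might infer that a met criterion rules out MD2. It blocks a higher-dose MD2, but 8.7.3 still allows reduced or repeat levels.
- A reader might infer that MD1 peaks exceed any already given. The estimate is 76% to 82% of the highest single-dose peak; what is new is repetition and duration.

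The reply does not supply a rule. The discretionary powers name no trigger, and SAE reporting need not pick up the two-subject criteria: confirmed QTc, creatinine, liver or blood-count findings in two subjects can meet one without either being an SAE.

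**Conclusion.** The point holds as a gap in the rules. Followed as written, a criterion met during MD1, MD2 or Cohort 7 does not pause the other subjects' dosing, and the scheduled SRC review of MD1 comes after its fourth dose. The gap covers up to 18 active MD1 doses and up to 6 RA patients. The documents do not say how many of these remain, so the present reach may be smaller; it applies equally to MD2 if that cohort runs.

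The reading of the text needs no assumption. The dose counts assume that all six active subjects stand at the same dose. The exposure estimates rest on a 19-day half-life and dose proportionality. All event rates are assumed, because the documents give none. The amendment should be made: it is cheap, and in a first-in-human trial a reversible pause costs less than a dose that cannot be withdrawn.

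**What to change.** In 8.7.2 add: *If events matching any criterion occur in Part 2 or Part 3, counted blinded regardless of treatment assignment, all further study drug dosing (undosed Cohort 7 patients and remaining MD doses) is paused at all sites until an ad hoc SRC review, which may unblind the cases to decide whether the criterion is met in SOL-116 recipients.*

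Also:

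- Keep the two-or-more-subjects wording without a per-cohort limit. A limit would narrow the present text, which can count one MD1 subject and one RA patient together.
- Add pausing or stopping dosing to the SRC determinations in 8.7.1.
- State that repeat or reduced dosing under 8.7.3 may begin only after that review.
- State whether a paused MD dose is given late or skipped.

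The blinded count is needed because the criteria refer to SOL-116 recipients and the sites do not know who they are.

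**Cost.** Amendment text, with no change in sample size. The price is false pauses. At an assumed 2% rate, each one-subject criterion triggers in about 14.9% of cohorts. The eight two-subject criteria together trigger in about 15% over two cohorts if counted within each cohort, and about 28% if pooled over both, assuming independence. Lower rates reduce these quickly.

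A paused dose may also miss its visit window (±1 day at Day 29, ±3 days at Days 57 and 85). On the instant-absorption model, exposure after dose 3 is 1.490 relative to dose 1. A 7-day delay before dose 4 then gives 1 + 2^(−35/19) × 1.490 = 1.416, about 8% below 1.536; a 14-day delay gives 1 + 2^(−42/19) × 1.490 = 1.322, about 14% below.
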